9.4.2 Percentage of Necrotic Tissue and "Complete Debridement"

All wound photographs will be reviewed in a blinded fashion, identified only by subject number, initials, and date of assessment by two independent reviewers. The reviewers will complete an assessment form providing the percentage of the ulcer covered by non-viable, neerotic tissue as measured using the ImageIQ EDCIQ mobile imaging system. In any case where one reviewer selects 0% or "complete debridement", and the second reviewer does not, the photograph will be re-reviewed at a consensus meeting.

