10. STATISTICAL DESIGN

A formal Statistical Analysis Plan (SAP) (also referenced to as the Statistical Considerations) will be written and finalized prior to database lock. The SAP will detail the summaries and analyses to be performed.

Smith & Nephew Wound Management Global Medical and Clinical Affairs Department will conduct data management and statistical analysis. Unless otherwise stated, all significance tests and hypothesis testing will be two-sided, performed at the 5% significance level. Resulting p-values will be quoted and 95% two-sided confidence intervals will be generated where appropriate. All analyses will be performed in SAS v9.4 (or later).

Where data summaries are specified, categorical and ordinal variables will be summarized using frequency distributions which will detail the number and percentage of subjects which fall into each category. Continuous variables will be summarized using the following summary statistics: mean, median, standard deviation, minimum and maximum values, and number of observations.

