10.3 EFFICACY

10.3.1 Primary Efficacy

The primary endpoint of the study is the proportion of subjects achieving complete debridement over the 6-week treatment period and will be analyzed as follows using the Full Analysis Set. For purposes of the primary analysis, the status of complete debridement will be assessed from photographs by two independent reviewers. In the event of disagreement between the two reviewers, the complete debridement status agreed during the consensus meetings will be analyzed in the primary analysis. In cases where a photograph is not taken, the Last Observation

Carried Forward (LOCF) method will be used. Sensitivity analyses will be conducted as detailed in the following sections.

An initial logistic regression model will contain covariates for treatment, baseline (defined as Study Visit 1) ulcer area, baseline percentage of nonviable tissue, and duration of ulcer. A forward selection procedure will be used for the addition of other baseline covariates with an F-value to attain a significance level of 0.1. Further baseline covariates to be assessed as part of this procedure include: subject age, baseline (maximum) ulcer depth, baseline PUSH and WBS scores.

The resulting analysis presented will correspond to the final model from the forward selection procedure. The results for the initial model will also be presented. For each of the effects in the initial and final model, the p-value, odds-ratio and corresponding 95% confidence interval will be presented. Secondary subgroup analyses may be conducted as a result of the covariate analyses. Additionally, treatment will be fitted on its own in a further logistic regression model. In each case, the residuals will be examined for outliers using influence plots of diagnostic statistics; further details are included in the SAP.

Cross-tabulations of each of the covariates (continuous covariates will be categorized for purposes of the cross-tabulations) with treatment and achievement of complete debridement, will be generated for each of the baseline covariates included in the final model.

The 95% confidence interval (unadjusted for all covariates) for the difference between treatments in proportion achieving complete debridement within 6 weeks will be generated along with the Chi-square or Fisher's Exact test p-value using the Per Protocol population depending on minimum expected cell.

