Two separate sensitivity analyses will be performed to ensure that the efficacy findings are not reliant on assumptions made in the analysis, derivations, or changes agreed between the blinded review panel. The analysis for the proportion of subjects achieving completed debridement will be repeated with the following modifications using the Full Analysis Set only:

- 1) In cases where there is initial disagreement (pre-consensus meeting) between the two blinded reviewers, the "worst case" value will be used. That is, in cases where one reviewer found the ulcer to have achieved complete debridement whilst the remaining reviewer found there to still be (>0%) necrotic, non-viable tissue present, the following will be imputed:

 Complete debridement achieved = No.
- 2) In cases where there is initial disagreement (pre-consensus meeting) between the two blinded reviewers, the "best case" value will be used. That is, in cases where one reviewer found the ulcer to have achieved complete debridement whilst the remaining reviewer found there to still be (>0%) necrotic, non-viable tissue present, the following will be imputed:

Complete debridement achieved = Yes.

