11. SAMPLE SIZE JUSTIFICATION

A previous study (7) with a design essentially identical to the present study demonstrated highly significant differences between treatment groups for achievement of complete debridement (85% vs. 29%, P<0.003), reduction in % area of non-viable tissue for each week (P<0.002), and in reduction in wound area (P<0.009). The sample size of this previous trial was 27 subjects, 13 in the SANTYL group, and 14 in the hydrogel group. Based on the reported outcomes in the previous trial, 26 subjects are required to detect a difference in the primary endpoint: the proportion of ulcers achieving complete debridement during the 6-week treatment period. This relates to a Fisher's Exact test assuming 85% vs 29% in the proportion of ulcers achieving complete debridement. To allow for 15% drop-out rate throughout the 6-week treatment period, a total of 32 subjects will be randomized (16 per treatment) in an equal allocation ratio for SANTYL and hydrogel. In the previous studies quoted, the secondary endpoints including reduction in % area of non-viable tissue and reduction in wound area were found to reach significance with similar numbers.

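### The two reader-disagreement sensitivity analyses recode disputed ulcers the same way in both arms, so they do not bound the treatment difference when both arms contain disputes

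*Combined protocol and SAP*

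**What the plan says.** Two blinded readers assess each photograph. Under section 9.4.2, if one records complete debridement and the other does not, "the photograph will be re-reviewed at a consensus meeting". Under section 10.3.1, "the complete debridement status agreed during the consensus meetings will be analyzed in the primary analysis".

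Section 10.3.1 then repeats the analysis twice in the Full Analysis Set. Where there was initial disagreement "between the two blinded reviewers, the 'worst case' value will be used", meaning that the ulcer counts as not debrided; the second run uses the best case and counts it as debrided. Neither rule mentions treatment arm. The stated purpose is "to ensure that the efficacy findings are not reliant on assumptions made in the analysis, derivations, or changes agreed between the blinded review panel". Section 10.3.2 reuses the pair for time to complete debridement. The text available contains no arm-opposed or tipping-point coding.

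**The concern.** The primary question is about a difference between arms. A worst case applied to both arms is the worst case for each arm's rate, not for the difference. The result is most exposed when consensus went to debrided on SANTYL and to not debrided on hydrogel. The first planned run then undoes only the SANTYL decisions and the second only the hydrogel decisions. Neither undoes both.

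With 16 subjects randomized per arm, one or two decisions per arm can move the primary p-value across 0.05. Both planned runs could stay significant and be read as showing independence from the panel, although a different set of consensus decisions would have given a non-significant result.

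**Working it through.** **Inputs.** Section 10: "all significance tests and hypothesis testing will be two-sided, performed at the 5% significance level". Section 11: "This relates to a Fisher's Exact test assuming 85% vs 29% in the proportion of ulcers achieving complete debridement"; 26 evaluable subjects; 32 randomized, 16 per arm. The documents give no number of disputed ulcers, so it is assumed below.

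**The plan's own figure.** Exact Fisher power at 85% v 29%, two-sided 0.05, is 74.2% with 12 per arm, 80.9% with 13 and 86.0% with 16. So 13 per arm (26 in total) is the smallest size that reaches 80%; that target is inferred, since section 11 states no power. Drop-out: 26/0.85 = 30.6, so 31, or 32 for equal arms. The plan's figures reproduce.

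**Why the pair is not a bound.** With n per arm, let s and h be the undisputed successes on SANTYL and hydrogel, and d_S and d_H the disputed ulcers. The difference in proportions, multiplied by n, is:

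- all disputed = No: s − h
- all disputed = Yes: s − h + d_S − d_H
- opposed, against SANTYL: s − h − d_H
- opposed, for SANTYL: s − h + d_S

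The last two are the extremes. If d_S or d_H is zero, they coincide with the two planned runs and the planned pair is enough. If both are positive, both planned runs lie strictly inside the extremes. If d_S = d_H, the two planned runs give the same difference.

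**Worked example.** Section 10.3.1 includes a logistic model with treatment alone. For a v b successes out of n = 16 per arm, log OR = ln[a/(n−a)] − ln[b/(n−b)], SE = √[1/a + 1/(n−a) + 1/b + 1/(n−b)], and z = log OR/SE. Take s = 12, h = 5, d_S = d_H = 2, with consensus Yes for both SANTYL disputes and No for both hydrogel disputes.

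| Coding | Successes | Difference | log OR | SE | Wald p | Fisher p |
|---|---|---|---|---|---|---|
| Consensus | 14 v 5 | 9/16 = 56 points | 2.734 | 0.929 | 0.003 | 0.003 |
| Planned worst case | 12 v 5 | 7/16 = 44 points | 1.887 | 0.790 | 0.017 | 0.032 |
| Planned best case | 14 v 7 | 7/16 = 44 points | 2.197 | 0.909 | 0.016 | 0.023 |
| Opposed, against SANTYL | 12 v 7 | 5/16 = 31 points | 1.350 | 0.766 | 0.078 | 0.149 |

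For the last row the likelihood-ratio test gives 0.069 and chi-square 0.072, so the loss of significance does not depend on the choice of test. The planned runs both show 44 points, while the disputes allow anything from 31 to 56.

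**Configurations where the test matters.** With 16 per arm, an opposed result of 12 v 6 is non-significant by Fisher (0.073) but significant by Wald (0.038), likelihood ratio (0.030) and chi-square (0.033). With 13 per arm and one dispute per arm (s = 10, h = 4), the planned runs give Wald 0.024 and 0.023. The opposed 10 v 5 gives Wald 0.055, Fisher 0.111, likelihood ratio 0.044 and chi-square 0.047.

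**How often.** Simulation at 85% v 29%, 16 per arm, each subject disputed with a fixed probability independent of arm and outcome (assumed). Among trials significant on consensus and on both planned runs, the share that loses significance under the coding against SANTYL is:

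| Assumed dispute rate | Logistic Wald | Fisher |
|---|---|---|
| 5% | about 5% | 7% |
| 10% | about 18% | 23% |
| 15% | about 36% | 45% |
| 20% | about 55% | 64% |

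The Wald figures shift slightly with the treatment of tables that have an empty cell. Counting those tables as non-significant gives 19%, 38% and 58% at the three higher rates.

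**The case against.** Four points on the other side deserve weight.

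*The readers are blinded.* Sections 8.2 and 9.4.2 identify photographs by subject and date, not by treatment, so the panel cannot knowingly settle disputes by arm. This stands. It makes the arm-opposed coding a stress extreme that would arise by chance. It does not turn the planned pair into a bound.

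*The planned pair is meaningful.* Requiring both readers to agree, or accepting either one, are rules that a blinded panel could actually apply. This also stands, and both runs should be kept.

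*The pair does detect dependence on consensus in many cases.* A reader might infer that it can never do so. That is wrong. When all disputes fall in one arm, the pair contains the arm-opposed result exactly. Among simulated trials that were significant on consensus but not under the opposed coding, at least one planned run had already lost significance in 48% to 61% (Wald) at dispute rates of 5% to 20%. The pair can miss cases; it does not miss all of them.

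*The plan sets no rule that two significant p-values mean robustness.* Correct. A reader might infer that the trial will be declared robust on that basis, but section 10.3.1 states only a purpose, and section 10 leaves detail to a SAP to be finalized before database lock. What remains is that the stated purpose, to ensure the finding does not rely on panel changes, is more than these two runs can deliver.

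**Conclusion.** The concern holds in a limited form. When both arms contain disputed ulcers, the two planned analyses do not bound the treatment difference and can both stay significant while a different set of consensus decisions would not. Two disputes per arm are enough under the treatment-only logistic model with 16 per arm. In simulation the gap is small at a 5% dispute rate (about 5% of otherwise consistent trials) and large at 20% (about 55%).

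This rests on assumed dispute rates, disputes independent of arm and outcome, one disputed status per subject, and the planning rates of 85% and 29%. The covariate-adjusted model cannot be recomputed from the documents. The opposed codings are exact extremes for the unadjusted difference, which need not carry over exactly to an adjusted odds ratio.

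Nothing here suggests that consensus decisions will favour an arm, and the primary estimate is unaffected. The weakness lies in the support for a robustness claim. It is worth correcting before database lock.

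**What to change.** In section 10.3.1:

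1. Keep the two planned analyses and describe them as strict-reader (both must agree) and lenient-reader (either suffices) rules.
2. Add the arm-opposed pair in the same model: disputed SANTYL = No with disputed hydrogel = Yes, and the mirror image. State that these are the extremes for the treatment difference and that, because reading is blinded, they are stress limits rather than likely outcomes.
3. Report by arm the number of subjects with an initial disagreement and how many were settled each way at consensus.

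If the added pair is not wanted, soften the stated purpose, because the two existing runs cannot ensure what it says. Where section 10.3.2 reuses the pair for time to debridement, the same addition can be made or the same limit stated.

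The cost is two more runs of an existing program and a short table, with no new data. The downside is a wider and less favourable reported range.

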10.3.2 Secondary Efficacy

The secondary efficacy variables include the time (in days) to achieve complete debridement, the percentage reduction in non-viable necrotic tissue for each assessment visit, and the percentage reduction in ulcer area for each visit and the change in wound status as measured by the PUSH and WBS tools following 6 weeks of treatments.

Time (in days) to achieve complete debridement during the 6-week treatment period (with complete debridement as defined in the primary analysis)

Once a subject has achieved complete debridement, the time to complete debridement will be calculated from the date of the randomization visit to the date at which the subject's ulcer was deemed to achieve complete debridement:

(Date of first complete debridement visit - Date of Randomization (SV1))

For those subjects that withdraw or do not achieve complete debridement during the study, the time to complete debridement will be censored at the last visit date attended. The resulting time to complete debridement will be defined as:

(Date of Last Study Visit attended - Date of Randomization (SV1))

Where the censored time to complete debridement is greater than 42 days, this will be truncated to 42 days.

A proportional hazards survival analysis will be applied to the time to achieve complete debridement using the Full Analysis Set. An initial proportional hazards model will include the covariates for treatment, baseline (defined as Study Visit 1) ulcer area, baseline percentage of nonviable tissue, and duration of ulcer. A forward selection procedure will be used for the addition of other baseline covariates with an F-value to attain a significance level of 0.1. Further baseline covariates to be assessed as part of this procedure include: subject age, baseline (maximum) ulcer depth, baseline PUSH and WBS scores. The resulting analysis presented will correspond to the final model from the forward selection procedure. The results for the initial model will also be presented. For each of the effects in the initial and final model, the p-value, hazard-ratio and corresponding 95% confidence interval will be presented. Secondary subgroup analyses may be conducted as a result of the covariate analyses. Additionally, treatment will be fitted on its own in a further proportional hazards survival analysis.

Further details, including model assumptions and diagnostics to be examined are included in the study SAP. The preceding analysis will be repeated using the Per Protocol Population.

Kaplan-Meier plots will be presented by treatment, baseline wound area strata, baseline percentage of nonviable tissue and ulcer duration (categorized) and also to represent all covariates with significant effects in the final survival analysis model. Individual plots for multiple factors will be generated where appropriate.

In addition, a sensitivity analysis will be performed to ensure that the efficacy findings are not reliant on assumptions made in either the analysis or derivations. For purposes of the sensitivity analysis, the time to confirmed complete debridement for those subjects discontinuing the treatment period prematurely will be censored at the maximum possible duration of treatment under the study protocol (42 days), rather than time of actual discontinuation. Lastly, the two sensitivity analyses defined in the proportion of subjects achieving complete debridement analysis will be repeated for the time to achieve complete debridement; in these cases the

censoring flag may be modified as detailed previously in the primary analysis, but the time in days will remain unchanged.

The percentage reduction in wound area over the 6-week treatment period and at each assessment visit

Wound area is defined as surface area as measured by the ImageIQ EDCIQ mobile imaging system at each assessment visit by two independent image reviewers. The percentage change in wound area over the 6-week treatment period is then defined as:

Percentage reduction in wound area over 6-week treatment period= $\left(\frac{Area_{SV1} - Area_{SV1}}{Area_{SV1}}\right) \times 100\right)$

In cases where the wound is closed in the opinion of the Investigator, the wound area will be imputed as 0 cm², resulting in a percentage reduction in wound area of 100%. In circumstances where the wound area is missing at the Study Visit 7 for subjects that have not withdrawn prematurely due to closure, the last observation carried forward (LOCF) method will be used.

An initial linear regression model will contain covariates for treatment, baseline (defined as Study Visit 1) ulcer area, baseline percentage of nonviable tissue, and duration of ulcer. A forward selection procedure will be used for the addition of other baseline covariates with an F-value to attain a significance level of 0.1. Further baseline covariates to be assessed as part of this procedure include: subject age, baseline (maximum) ulcer depth, baseline PUSH and WBS scores. The resulting primary analysis presented will correspond to the final model from the forward selection procedure. The results for the initial model will also be presented. For each of the effects in the initial and final model, the p-value, parameter estimate and corresponding 95% confidence interval will be presented. Secondary subgroup analyses may be conducted as a result of the covariate analyses. Additionally, treatment will be fitted on its own in a further linear regression model. The potential for interactions will be examined by fitting the required interaction terms in addition to those effects in the final linear regression model from the forward selection procedure. In each case if the residuals are not normally distributed then non-parametric bootstrapping will be applied. If the nonparametric bootstrap estimates of the confidence intervals for the difference in mean percentage reduction in area between treatments

differ considerably to the standard model estimates, then the nonparametric bootstrap estimates will be used.

The percentage reduction in wound area over the 6-week treatment period will be summarized by treatment separately by the covariates used in the final model.

In addition, a two-sample t-test will be used to test for a difference between treatments in the mean percentage reduction in wound area between Visit 1 and Visit 2. The test will be repeated for comparisons between Visit 1 and Visits 3, 4, 5 and 6 individually. In each case, if normality assumptions do not hold, a Wilcoxon Rank Sum test will be used.

The wound area, reduction in wound area and percentage reduction in wound area at each study visit will be summarized by treatment separately by baseline wound area strata and overall.

The reduction in percentage non-viable necrotic tissue over the 6-week treatment period and at each assessment visit

For purposes of the analysis, the assessment of percentage non-viable necrotic tissue will be assessed from photographs by two independent reviewers. The following analysis uses the mean of the two percentage non-viable tissue assessments conducted by the independent reviewers for each visit. In the event of disagreement between the two reviewers, the percentage non-viable necrotic tissue used in the following analysis will be the mean of the individual assessments of non-viable necrotic tissue after any consensus meetings have been conducted.

The reduction in the percentage non-viable necrotic tissue will be derived as:

Percentage non-viable necrotic tissue at Study Visit 1 – Percentage non-viable necrotic tissue at Study Visit 7

In cases where a photograph is not taken, the Last Observation Carried Forward (LOCF) method will be used. Sensitivity analyses will be conducted as detailed in the following sections.

The linear regression analysis described in the previous section to test for a difference between treatments in the percentage reduction in wound area over the 6-week will be repeated for the reduction in percentage of non-viable necrotic tissue over the 6-week treatment period. In addition, the separate analysis conducted to test for a difference in percentage reduction in

wound area between treatments between Visit 1 and Visits 2,3,4,5 and 6 will be repeated for the reduction in percentage of non-viable necrotic tissue at the stated time points.

The reduction in percentage non-viable necrotic tissue over the 6-week treatment period will be summarized by treatment separately by the covariates used in the final model. In addition, the percentage non-viable necrotic tissue and reduction percentage non-viable necrotic tissue at each study visit will be summarized by treatment separately by baseline percentage necrotic tissue [categorized] and overall.

Two separate sensitivity analyses will be performed to ensure that the efficacy findings are not reliant on assumptions made in the analysis, derivations or changes agreed between the blinded review panel. The previous section will be repeated with the following modifications using the Full Analysis Set only:

- The "worst case" value will be used. That is, the highest value of percentage non-viable necrotic tissue recorded by the two independent reviewers at each time point will be used for purposes of analysis.
- 2) The "best case" value will be used. That is, the lowest value of percentage non-viable necrotic tissue recorded by the two independent reviewers at each time point will be used for purposes of analysis.

Change in Wound Status as measured by the PUSH and WBS tools following 6 weeks of treatment

Wound status will be measured by both the PUSH and WBS tools at Study Visit 1 and at Study Visit 7 (Exit).

At both Study Visit 1 and Study Exit, the PUSH Tool (version 3.0) will be scored according to the instructions for use (18.1.1). The sub-scores for Length/Width, Exudate Amount, and Tissue Type will be recorded. The Total Score, on a scale of 0-17, will then be derived by taking the sum of the three sub-scores detailed previously.

The reduction in PUSH individual sub-scores will be derived as follows; the reduction in Total Score will be derived using the same method:

PUSH Score at Visit 1 - PUSH Score at Exit Visit

A Wilcoxon Rank Sum test will be used to test for a difference between treatments in the reduction in Total PUSH Score over the 6-week treatment period.

The responses to the individual sub categories (Length/Width, Exudate Amount, and Tissue Type) will be summarized by treatment at each visit; in addition the reduction over the 6-week treatment period in each sub-score and total score will be summarized by treatment.

The WBS will be scored at the Study Visit 1 and Study Exit according to the instructions for use (18.1.2). The individual wound bed score characteristics, on a scale of 0-2, will be summed to derive the Total WBS on a scale of 0-16.

The reduction in Total WBS will be derived as follows:

Total WBS Score at Visit 1 - Total WBS Score at Exit Visit

A Wilcoxon Rank Sum test will be used to test for a difference between treatments in the reduction in Total WBS over the 6-week treatment period.

The responses to the individual wound bed score characteristics (Healing edges, Black eschar, etc.) will be summarized by treatment at each visit.

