This visit should occur no more than 7 days after the Screening Visit. Any subject who returns but does not qualify at this visit will be a screen failure and will not be randomized. Upon completion of all screening procedures and confirmation that the subject is eligible for the study, the Investigator or designee will randomize the subject using an electronic randomization system (www.sealedenvelope.com) to obtain the treatment assignment.

The day of the week (Monday, Tuesday, etc.) on which this visit occurs will set the weekly visit day for all subsequent assessments/visits (Study Visits 2 through 7) if the subject is randomized. A (± 1) day visit window will be allowed. If an assessment is not made on the original day of the week for Study Visits 2-7, subsequent visits should be scheduled on the original week day. To minimize differences in baseline ulcer size between the two groups, randomized subjects will be stratified by ulcer size determined at this visit [≥ 1.0 and ≤ 10.0 cm²; ≥ 10.0 and ≤ 64.0 cm²]. Once randomized, subjects will be assessed weekly for the duration of the treatment period (SV1 through SV7).

The following procedures will be completed:

- 1. Record any changes in general health and the use of concomitant medications.
- 2. If any adverse events are observed or reported, they must be recorded as instructed in Section 12, *Adverse Events*.
- Review laboratory results from the blood sample and all other inclusion/exclusion
 criteria.
 - If the blood test results qualify and all entry criteria are met, the subject may be randomized.
- Irrigate the wound with normal saline delivered at 4-15 psi using the Irrimax® device.
 (Sharp debridement is NOT allowed.)
- 5. Photograph the target ulcer using the ImageIQ EDCIQ mobile imaging system. The target ulcer area (cm²) and percentage of the target ulcer surface covered with necrotic, nonviable tissue will be determined by two independent reviewers using the ImageIQ EDCIQ mobile imaging system. The target ulcer area and percentage of necrotic, nonviable tissue must be assessed by at least one independent reviewer prior to the subject being randomized.

Note: If the area of the target ulcer is >64.0 cm², the subject must be screen failed and should not be randomized.

- 6. Assess the wound status using both the PUSH and WBS tools.

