9.1.5 Unscheduled Visits

Unscheduled exams may be conducted at the discretion of the Investigator with all obtained information recorded in the source documents and on the Unscheduled Visit pages within the Case Report Form (CRF).

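### Time to complete debridement: weekly photograph dates enter the Cox model as exact event days, no tie method is named, and only censored times are cut off at day 42

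*Combined protocol and SAP*

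**What the plan says.** Section 8.1 and Table 17-1 place photography at screening and at Visits 1 to 7, one week apart after randomization. Section 9.1.2 adds: "A (± 1) day visit window will be allowed". Section 9.1.3 says that a visit outside the window is still carried out and logged as a deviation. Debridement status comes from two masked readers of the photographs (section 9.4.2).

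In section 10.3.2 the event time is "calculated from the date of the randomization visit to the date at which the subject's ulcer was deemed to achieve complete debridement". Subjects without the event are censored at their last attended visit, and a censored time beyond 42 days is cut back to 42. No such limit is set for event times. The model follows: "A proportional hazards survival analysis will be applied to the time to achieve complete debridement using the Full Analysis Set". It contains treatment, three baseline covariates and any others added by forward selection.

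The section names no tie method and no interval-censored or grouped-time model. Its sensitivity analyses change the censoring time of early discontinuations and the handling of disagreement between readers. Model assumptions and diagnostics are left to a SAP that, under section 10, need only be final before database lock. That SAP's text is not in the document reviewed.

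**The concern.** A photograph read as debrided shows only that the event happened since the last photograph read as not debrided. With six post-baseline photographs, all events fall on or near six days. Two things follow.

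- With so many ties, the estimated hazard ratio depends on how ties are handled, and that choice is left open.
- The ±1 day window orders subjects by appointment day within a week. At the last visit this meets the one-sided 42-day rule: subjects not debrided on day 43 are moved back to day 42, while subjects debrided on day 43 stay there.

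Time to debridement is the first-listed secondary objective. It is to be reported with a hazard ratio, confidence interval and p-value, in a trial meant to confirm an earlier result. At stake is the size of that hazard ratio, not the primary result.

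**Working it through.** **Inputs.** Rates of 85% v 29% by week 6, 26 evaluable and 32 randomized (section 11); two-sided 5% tests (section 10); weekly photographs (section 8.1); ±1 day (section 9.1.2); event, censoring and 42-day rules (section 10.3.2). Assumed: constant hazards, no dropout, visit shifts uniform on −1, 0, +1 day, and 80% planning power (not stated).

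**1. The plan's own figure.** Section 11 says "26 subjects are required to detect a difference in the primary endpoint" and "This relates to a Fisher's Exact test assuming 85% vs 29% in the proportion of ulcers achieving complete debridement". Exact power of the two-sided Fisher test is 74.2% at 12 per arm and 80.9% at 13 per arm, so 26 is reproduced at 80% power. Then 13/0.85 = 15.3, rounded up to 16 per arm, gives 32. The plan states no hazard ratio, event count or power for time to debridement.

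**2. True hazard ratio.** With constant hazards, λ = −ln(1 − p)/42, so HR = ln(0.15)/ln(0.71) = 5.54.

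**3. Events and ties.** Expected events are 16 × 0.85 + 16 × 0.29 = 13.6 + 4.64 = 18.2. In simulation about 94% of them are tied on an exact weekly grid, and about 65% with ±1 day windows.

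**4. Large-sample hazard ratio, true value 5.54** (six runs of 5,000 per arm)

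| Observation | Breslow | Efron | Discrete |
|---|---|---|---|
| Exact weekly grid | 4.90 | 5.54 | 6.34 |
| ±1 day windows, 42-day rule as written | 5.00 | 5.22 | 5.77 |

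A separate check gave 4.93 and 5.58 (Breslow, Efron) on the grid, and 4.98 and 5.20 with windows. Against 5.54, Breslow on the grid is 12% low (4.90/5.54 = 0.88). Efron with windows as written is 6% low (5.22/5.54 = 0.94).

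**5. Why Efron falls with windows.** Visit 7 falls on day 41, 42 or 43. Under section 10.3.2, subjects not debrided on day 43 are recorded as censored at day 42, so the risk set on day 43 holds only subjects with an event that day. Those events no longer count against the subjects who did not debride.

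- Capping events at 42 as well moved Efron from 5.23 to 5.51 in one check. In three runs of 20,000 per arm it moved from 5.05–5.13 to 5.32–5.46.
- Using the nominal week for both event and censoring times, with Efron ties, gave 5.53.

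**6. Size in this trial.** SE(log HR) ≈ √(1/13.6 + 1/4.64) = 0.54. The Breslow shift is ln(5.54/4.90) = 0.12, or 0.23 SE. The Efron-with-windows shift is ln(5.54/5.22) = 0.06, or 0.11 SE.

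At 16 per arm (1,500 trials, treatment only), power was 91.1% with Breslow and 93.3% with Efron on the grid, and 91.4% and 92.2% with windows. With no true effect (55% response in both arms) the hazard ratio stayed at about 1.01. Rejection was 3.3% to 5.3% across tie methods.

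**7. Which model to prefer.** With the three initial covariates simulated as noise at 16 per arm, small-sample inflation is larger than the tie effect. One check gave about 7.2 for a grouped complementary log-log model, 6.6–6.7 for Efron and 6.8 with continuous times. Another (500 runs, exact weeks) gave medians of 6.84 for the grouped model, 6.27 for Efron and 5.42 for Breslow. The grouped model spends six week terms and at least four covariate terms on about 18 events.

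**The case against.** The strongest reply is that the loss is small and partly hypothetical.

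- **Direction.** A reader might infer that tied times necessarily shrink the hazard ratio. The documents do not support that. They name no tie method, and on the weekly grid the result is low with Breslow, unbiased with Efron and high with a discrete model. The SAP could still settle the choice. This stands for ties. It does not cover the 42-day rule, which section 10.3.2 states in full and which lowers the estimate even under Efron.
- **Materiality.** The shifts are at most about a quarter of one standard error, and ties do not raise false positives. This stands, and it limits the weight of the point.
- **The obvious remedy.** A grouped-time model inflates the hazard ratio most at this sample size. This stands, so that model belongs in a sensitivity analysis.
- **Unscheduled exams.** Section 9.1.5 says "Unscheduled exams may be conducted at the discretion of the Investigator", and section 9.4.2 says "All wound photographs will be reviewed in a blinded fashion". A reader might infer that unmasked staff can bring the event forward by adding photographs in one arm. The documents do not say that photographs are taken at such exams, and Table 17-1 lists none. If they were, a mid-week photograph every week in one arm would move a null hazard ratio to about 1.06 or 0.95 at 55% response, and photographs in a quarter of weeks would move it 1–2%. Rejection stays at 4–5%. An extreme case, with one arm photographed twice weekly throughout and 85% response in both arms, gave 1.12. This supports a clarifying sentence, not a finding of bias.
- **Replication.** The objective is stated in days and is meant to match the earlier trial. Nominal visit days are still days, so the objective need not change.

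**Conclusion.** The point holds in a limited form. Section 10.3.2 treats a weekly reading as an exact day, leaves the tie method open, and handles events and censored times differently at day 42. At the protocol's planning rates the large-sample hazard ratio, truly 5.54, is about 4.9–5.0 if Breslow ties are used. With Efron it is about 5.5–5.6 on an exact weekly grid and about 5.2 with ±1 day windows as written. Naming Efron alone is therefore not enough.

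The consequence is a modestly understated secondary estimate and a power change of 1 to 3 points. False positives do not rise, and the primary analysis and its sample size are unaffected. The figures rest on constant hazards, no dropout and uniform visit shifts. The Breslow figure also rests on a tie method that the documents do not name.

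**What to change.** In section 10.3.2, and in the SAP:

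1. Set both event and censoring times to the nominal day of the scheduled week (Visits 2 to 7: days 7, 14, … 42). This caps both at day 42. If actual dates are kept instead, apply the 42-day cap to events as well as to censored times.
2. Fit the Cox model with Efron ties and name that method.
3. Add an interval-censored or grouped-time model as a sensitivity analysis only, since about 18 events cannot well support the extra week terms.
4. State that only photographs from scheduled visits date the event. Include the exit visit after early discontinuation or closure, and assign it to a nominal week by elapsed time under a rule fixed in advance. The label Visit 7 must not place an early exit at day 42.

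The cost is wording and one model statement, with no new data. The downside is that time is reported on a weekly grid rather than by actual visit date, so differences of a day or two between visit dates no longer show.
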